2.2.2 Primary Endpoint

The primary endpoint is the proportion of DEB primary wound sites with complete wound healing from baseline in B-VEC-treated and placebo-treated intra-subject wound sites at Weeks 22 and 24 or Weeks 24 and 26, as determined by the Investigator, to evaluate durability of response and repeat dosing. Complete wound healing is defined as 100% wound closure from the exact wound area selected at baseline, specified as skin re-epithelialization without drainage. If new neighboring wounds form around the original traced baseline wound during the primary and secondary evaluation time points, these wounds will not be included in the evaluation.

The primary endpoint is defined as wounds that meet any of the following conditions:

- Healed on Week 22 and Week 24, or
- Healed on Week 24 and Week 26

Only wounds that are healed for at least two (2) consecutive weeks are counted as positive responses.

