
Primary Endpoint
	
Wound Healing
 
The primary endpoint is the proportion of DEB primary wound sites with complete wound healing of the originally selected baseline wound in B-VEC versus placebo treated intra-subject wound sites at Weeks 22 and 24 or Weeks 24 and 26, as determined by the Investigator, to evaluate durability and repeat dosing. The complete wound healing is defined as 100% wound closure of the exact original wound surface area selected at baseline, specified as skin re-epithelialization without drainage.

Secondary Endpoints
	
Key Secondary Endpoint
 
 
• Proportion of the selected primary wound sites with complete wound healing of the exact wound surface area selected at baseline (as defined in the primary endpoint) in B-VEC-treated versus placebo at Weeks 8 and 10 or Weeks 10 and 12 (as determined by the Investigator) to evaluate durability.
 
 
Secondary Endpoint
 
 
• The mean change in pain severity using a VAS score per primary wound site associated with wound dressing changes at Weeks 22, 24 and 26 for each treated versus placebo wound, for ages 6 and above on the primary wound pair. For ages below 6 years, the Face Legs Activity Cry and Consolability-Revised (FLACC-R) scale will be used.
 

Exploratory Endpoints
	
 
• Relative time to wound closure from baseline.
 
• Duration of closure, as defined by the time from complete wound closure to the reopening of the Primary Wounds.
 
• The mean change in Quality of Life in addition to Skindex score as compared to baseline at Week 26.
 

Safety Endpoint
	
 
• The safety and tolerability of B-VEC based on the assessment of adverse events, physical examinations, vital signs, and clinical laboratory test results.
 

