#### 2.2.2.1 Primary Endpoint Rationale

[figure not shown]
The GEM-3 pivotal study has been designed as an adequate well-controlled clinical study per Agency guidance (21 CFR 314.126) to provide substantial evidence of product effectiveness. The double-blinded, placebo-controlled study design will minimize bias on the part of subjects, and Investigators. The FDA's guidance Gene Therapy for Rare Diseases (July 2018) suggests that an intra-subject control approach, for such rare skin diseases, may be a useful design. The wounds will be matched in respect to size and anatomical location.

Complete wound healing will be defined as complete closure of the initial wound surface selected at baseline, specified as skin re-epithelialization without drainage for two (2) consecutive weeks, as evaluated by the Investigator at Weeks 22 and 24 or 24 and 26. If new neighboring wounds form around the original traced baseline wound during the primary evaluation time points, these areas will not be included in the evaluation.

B-VEC is a transient non-integrating episomal vector that can be detected up to five days in B-VEC *in vivo* studies. The Phase I/II B-VEC completed study, that has evaluated different dosing regimens shows that continuous expression of COL7 during the wound healing process allows for durability of the healed wound with no safety outcomes. Therefore, a weekly dosing regimen has been proposed based on life span of B-VEC and results from the Phase I/II clinical study that would allow for functional restoration of COL7 at basement membrane zone. It has been shown that the half-life of human COL7 is approximately 30 days. Based on a half-life assumption of about one month for COL7, a residual protein amount of 25% should be present after two months (Kuhl, et al., 2016). It is known that about 30-40% of COL7 levels are needed to protect the skin from frictional damage (Kern, et al., 2009) (Kuhl, et al., 2016) and even lower levels of COL7 may improve the phenotype of full COL7 deficiency remarkably (Fritsch, et al., 2008) (Alexeev, et al., 2011) (Schweiger-Briel, et al., 2015). The basement membrane and its constitutive components undergo constant remodeling (Kivirikko, et al., 1996) which has implications for anchoring fibril turnover approximately every 60 days to 90 days (8 weeks to 12 weeks). Therefore, the proposed evaluation of the primary endpoint at Weeks 22 and 24 or 24 and 26, for two (2) consecutive weeks, is justified.

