**Figure 1. Change in Wound Area from Baseline in B-VEC vs. Placebo Treated in Phase I/II Study**

The usual pattern in a placebo response is often similar to active treatment with or without significant separation. Due to the nature of the DEB wounds, frequent closing and opening cycle is observed, therefore a fixed assessment may lead to a biased conclusion in comparing a normal treatment profile to an abnormal profile of a placebo response. To accommodate this variability of the placebo response, an assessment of two (2) consecutive weeks, at Weeks 22 and 24 or 24 and 26, are considered to evaluate durability of wound healing and frequency of repeat administration.

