##### 6.2.1.2 Investigator Assessment of Complete Wound Closure

Investigator Assessment of Complete Wound Closure will be performed at the time points indicated in the Schedule of Events ([Table 1](#)) after removal of subject's dressings from target wounds prior to any potential disruption of the target wounds (i.e., markings, bacterial culture of wounds for clinical purposes, or B-VEC administration).

The Investigator Assessment of Complete Wound Closure of Primary and Secondary wounds should be performed by the PI. A trained, medically qualified Sub-I should only perform if the PI is unavailable. Evaluator information will be recorded on the applicable assessments.

In order to reduce inter-evaluator variability, it is important that the same evaluator assess complete wound closure for the same subject at all study visits, whenever feasible. If it is not possible for the same evaluator to continue performing the assessment, it is recommended that the primary and subsequent evaluator both examine and discuss their respective scoring during at least one visit.

Wound healing will be defined as complete closure of the originally selected wound surface identified at baseline, specified as skin re-epithelialization without drainage, as evaluated by the Investigator. If new neighboring wounds form during the key evaluation time periods at Weeks 8, 10 12, 22, 24 and 26 those wounds will not be included in the wound closure evaluation. Primary efficacy wound assessment occurring at two (2) consecutive weeks at Week 22 and 24 or 24 and 26 will be assessed live, followed by a review against the 2D and 3D images.

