7.2.1 Sensitivity and Supplementary Analyses of the Primary Efficacy Endpoint

Sensitivity analyses of the primary endpoint include:

- The primary analysis described in Section [7.2](#) for the primary efficacy endpoint will be repeated for the PP and mITT populations.
- The primary analysis described in Section [7.2](#) for the primary efficacy endpoint will be repeated with observed data without any imputations for missing values (i.e., if a subject is missing either a B-VEC or placebo outcome, the subject will be excluded from the analysis).

Supplementary Analysis:

- Common treatment risk difference will be obtained from conditional logistic regression with covariates age and gender and stratified by subject (matched pair) and multiple imputation approach described in section [7.1.6](#) assuming MAR.

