7.3.1 Sensitivity and Supplementary Analyses of the Key Secondary Efficacy Endpoint

Sensitivity analyses of the key secondary endpoint include:

- The analysis described in Section 7.3 for the key secondary efficacy endpoint will be repeated for the PP and mITT populations.
- The key secondary efficacy analysis performed in Section 7.3 for the key secondary efficacy endpoint will be repeated with observed data without any imputations for missing values (i.e., if a subject is missing either a B-VEC or placebo outcome, the subject will be excluded from the analysis).

Supplementary Analysis:

- Common treatment risk difference will be obtained from conditional logistic regression with covariates age and gender and stratified by subject (matched pair) and multiple imputation approach described in section 7.1.6 assuming MAR.

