7.5 Additional Analysis

The wound healing data from wounds that are not from primary wound pair will be listed .

The change in patient reported outcomes such as Heath (EQ-5D-5L) and Skin Index (Skindex-29) before and after end of treatment will be summarized.

8 Safety and Tolerability

All safety analyses will be conducted in the Safety population. Safety measures include adverse events, physical examinations, vital signs, and clinical laboratory tests.

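### Does the phrase about two consecutive weeks of healing claim more than the two-visit responder rule can show?

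*SAP*

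**What the plan says.** The responder rule is two bullets followed by a sentence. SAP 2.2.2 and 7.2 count a primary wound as healed if it is closed at Weeks 22 and 24, or at Weeks 24 and 26. SAP 2.2.3 and 7.3 use Weeks 8 and 10, or 10 and 12. Each then adds: "Only wounds that are healed for at least two (2) consecutive weeks are counted as positive responses". The same sentence stands in the protocol Synopsis (twice) and in protocol 2.2.2, 2.2.3, 8.1, 8.2, 8.7.2 and 8.7.3. That makes 12 copies, 4 in the SAP and 8 in the protocol, not counting the amendment summary.

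Protocol 2.2.2.1 explains the pairing of visits. In these wounds a "frequent closing and opening cycle is observed", so a single fixed visit might mislead. The same section defines complete healing as closure "for two (2) consecutive weeks, as evaluated by the Investigator at Weeks 22 and 24 or 24 and 26", and protocol 6.2.1.2 speaks of the "Primary efficacy wound assessment occurring at two (2) consecutive weeks at Week 22 and 24 or 24 and 26".

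The Schedule of Events allows ±3 days per visit. Its footnote 7 limits formal closure assessment of the primary wounds to Weeks 8, 10, 12, 22, 24 and 26.

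**The concern.** The sentence reads as two weeks of sustained healing, whereas the rule observes two points in time. A wound closed at Week 22, open at Week 23 and closed again at Week 24 is a responder. The endpoint is meant to speak to durability, and the sponsor's own rationale expects wounds to open and close.

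Nothing in the SAP addresses the interval. The lists that begin "Sensitivity analyses of the primary endpoint include" (SAP 7.2.1) and "Sensitivity analyses of the key secondary endpoint include" (SAP 7.3.1) vary the population and the handling of missing data, and each adds one supplementary model. SAP 7.5 says "The wound healing data from wounds that are not from primary wound pair will be listed", which leaves out the primary pair. The protocol's exploratory endpoint, "Duration of closure, as defined by the time from complete wound closure to the reopening of the Primary Wounds", has no analysis in the SAP. At stake is how far a durability statement could be pressed from the responder rates.

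**Working it through.** **Interval between qualifying visits.** Nominal spacing is 14 days, with ±3 days at each end.

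- Shortest: 14 − 3 − 3 = 8 days. Longest: 14 + 3 + 3 = 20 days.
- If each visit is instead timed 7 ± 3 days from the one before: 2 × 4 = 8 to 2 × 10 = 20 days, the same range.

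So the literal reading is not guaranteed by the rule.

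**The plan's own figure.** SAP 3.1.3 gives 24 pairs for 90% power at response rates of 75% and 25%, with independent wounds. The discordant cells are 0.75 × 0.75 = 0.5625 and 0.25 × 0.25 = 0.0625. Exact enumeration of the two-sided McNemar test gives power 0.888 at 23 pairs and 0.905 at 24, so 24 is reproduced. It rests on the responder rates and does not depend on how the sentence is read.

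**Is the rule ambiguous?** In all 12 places the visits are listed directly above the sentence. Protocol 2.2.2.1 and 6.2.1.2 attach the phrase to the same visit pairs. A programmer would code closure at both visits of either pair. The alternative, continuous closure, could not be coded from the formal assessments, because none is scheduled at Weeks 9, 11, 23 or 25.

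**What would requiring the middle visit do?** The documents give no reopening rates, so this is illustration only. Assume a stationary two-state weekly process with closed share *p* and week-to-week correlation *r*. Then:

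- closed one week away, given closed: q1 = p + r(1 − p)
- closed two weeks away, given closed: q2 = p + r²(1 − p)
- weekly reopening: (1 − p)(1 − r)
- responder under the plan: p[1 − (1 − q2)²]
- responder if the middle visit must also be closed: p[1 − (1 − q1²)²]

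*Example A: closed shares set to 75% and 25%, both arms reopening at 20% per week.* For B-VEC, r = 0.2, q1 = 0.80 and q2 = 0.76, so the rate goes from 0.75 × 0.9424 = 0.7068 to 0.75 × 0.8704 = 0.6528. For placebo, r = 0.733, q1 = 0.80 and q2 = 0.653, so it goes from 0.2200 to 0.25 × 0.8704 = 0.2176. The risk difference falls from 48.7 to 43.5 points.

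*Example B: closed shares chosen so that the plan's rule returns exactly 75% and 25%, with r = 0.5 in both arms.* For placebo, p = 0.333, q1 = 0.667 and q2 = 0.5, so the rate goes from 0.250 to 0.230. For B-VEC, p = 0.772, and the rate goes from 0.750 to 0.737. The risk difference rises from 50.0 to 50.6 points.

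| Assumption | Planned rule | Middle visit required | Change (points) |
|---|---|---|---|
| Closed 75/25, both reopen 20% | 48.7 | 43.5 | −5.2 |
| Closed 75/25, reopening 10% B-VEC, 30% placebo | 53.8 | 53.8 | about −0.05 |
| Closed 75/25, reopening 10% B-VEC, 60% placebo | 61.0 | 64.9 | +3.9 |
| Responders 75/25, r = 0.2 both | 50.0 | 53.3 | +3.3 |
| Responders 75/25, r = 0.5 both | 50.0 | 50.6 | +0.6 |
| Responders 75/25, r = 0.7 both | 50.0 | 50.1 | +0.1 |

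The sign turns on the assumptions. In the calibrated cases with equal correlation, for r from 0 to 0.9, power at 24 pairs with the SAP's test stays between 0.94 and 0.99.

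**Could the middle visit be analysed?** Protocol 4.2.7 and 4.2.9 list closure assessment at Weeks 23 and 25 for secondary wounds only, and 4.2.5 does the same for Weeks 9 and 11. The weekly dosing judgement takes the wound and its neighbours together (SAP 2.2.1), and nothing says it is stored as an open/closed variable. The healed box in the imaging software is optional (protocol Appendix 1). A judgement of closed would confirm that the baseline area was closed. A judgement of open would not show that it had reopened, because neighbouring wounds, which the endpoint excludes, can produce it.

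**The case for a change.** The strongest case for a change is that rewording costs little and would state exactly what is observed: closure at two assessments scheduled two weeks apart. A reader who meets the sentence alone may take it for sustained healing. Because the effect of reopening is unknown in both size and direction, there is an argument for fixing an analysis of the middle visit in advance, counting ambiguous visits first as open and then as closed.

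Part of this stands. The sentence is loose, the 8-to-20-day interval is correct, and the SAP has no analysis of the interval. But the sentence never stands without its bullets, so the rewording alters no result, and 8 of the 12 copies would need a protocol amendment. The two-way analysis would yield a range driven partly by neighbouring wounds, from data not shown to be recorded. It would also add only one more time point, and the qualifying visits could still be 8 days apart. The missing SAP analysis of duration of closure is a separate omission and does not make this rule wrong.

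**Conclusion.** No change is needed. The sentence is shorthand for paired visits two weeks apart, and the bullets beside it settle the programming. Both wounds of a pair follow the same visit schedule and rule, so the McNemar comparison, its type I error and the power at 24 pairs are untouched. Using two visits rather than continuous observation is a fair trade-off for wounds that cycle, and the protocol gives that reason.

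What remains is a limit on interpretation: the responder rate shows closure at two assessments 8 to 20 days apart and does not prove unbroken closure. Analysts can report it that way without altering the plan. Weekly images of open and closed wounds are kept if a particular responder is questioned. The possible shift in the risk difference, −5.2 to +3.9 points in the cases shown, rests wholly on assumed reopening rates. It is neither a bound nor evidence of bias in either direction.

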2.2.3 Key Secondary Endpoint

The key secondary endpoint is defined as the proportion of primary wound sites with complete wound healing from baseline (as defined in the primary endpoint) in B-VEC-treated versus placebo at Weeks 8 and 10 or Weeks 10 and 12 (as determined by the Investigator). Complete wound healing is defined as 100% wound closure of the originally selected wound area at baseline, specified as skin re-epithelialization without drainage. If new neighboring wounds form around the original traced baseline wound during the key secondary evaluation time points, these areas will not be included in the evaluation.

The key secondary endpoint is defined as wounds that meet any of the following conditions:

- Healed on Week 8 and Week 10, or
- Healed on Week 10 and Week 12

Only wounds that are healed for at least two (2) consecutive weeks are counted as positive responses.

2.2.4 Secondary Endpoints

The secondary endpoint is the mean change in pain severity using a VAS score per primary wound site associated with wound dressing changes at Weeks 22, 24, and 26 for ages 6 and above on the Primary Wound Pair. For ages below 6 years, the Face Legs Activity Cry and Consolability-Revised (FLACC-R) scale will be used.

2.2.5 Safety Endpoints

The safety and tolerability of B-VEC based on the assessment of adverse events, physical examinations, vital signs, and clinical laboratory test results.

3 Study Implementation

Blood tests, or medical interventions may occur at the discretion of the Principal Investigator due to clinical changes that require evaluation or therapy. Detailed information for the study visits is provided in the sections below and in the Schedule of Events ([Appendix 1](#)).

3.1 Study Design

GEM-3 is a multi-center, intra-subject randomized, placebo-controlled, double-blind, Phase III study of B-VEC for the topical treatment of DEB wounds. A schematic of the study design is shown in [Figure 1](#) below.

Figure 1. B-VEC-03 Study Design

B-VEC: Beremagene Geperpavec, single dose/wound administered 4×10^8 PFU B-VEC/wound ($<20 \text{ cm}^2$), 8×10^8 PFU B-VEC/wound ($20 \text{ to } 40 \text{ cm}^2$) or 1.2×10^9 PFU B-VEC/wound ($40 \text{ to } 60 \text{ cm}^2$), once a week for up to 26 weeks, Placebo, single matching dose/ wound administered once a week for up to 26 weeks.

3.1.1 Study Design Rationale

The primary objective is to determine whether administration of B-VEC in addition to standard of care improves wound healing as compared to placebo in children, adolescents, and adults with Dystrophic Epidermolysis Bullosa (DEB).

The FDA's guidance Gene Therapy for Rare Diseases (July 2018) suggests that an intra-subject control approach, for such rare skin diseases, may be a useful design. Based on our previous experience (completed B-VEC Phase I/II study) and suggestions from the guidance we will continue to use the intra-subject design in the Phase III study. Each subject will serve as their own control; subjects will have two matched wounds (primary wounds). The primary wounds will be randomized such that one wound will receive B-VEC (active treatment) and the other will receive placebo (inactive treatment). The secondary wounds will receive B-VEC (active treatment), not to exceed the Remaining Weekly Dose. Subjects who enrolled under previous protocol versions, where more than one wound pair was selected, the Investigator's determined a single pair, most closely matched in size, followed by location, to be used for efficacy analysis, following the Agency's guidance.

This Phase III protocol is designed to minimize subject burden by limiting blood draws and removing the collection of biopsies. Experience from the phase I/II portion of the B-VEC trial combined with the advice provided in the FDA's guidance Epidermolysis Bullosa: Developing Drugs for Treatment of Cutaneous Manifestations (June 2019) justifies the proposed design. Molecular correction evaluation from all of the subjects from the Phase I/II study have shown full length COL7 expression by Immuno-fluorescence (IF) (staining for both NC1 and NC2 antibodies) and/or anchoring fibrils by Immuno-electron microscopy (IEM). We believe that robust molecular correction has been demonstrated with wound healing hence the proposed Phase III will mainly focus on evaluation of wound healing as the efficacy endpoint.

3.1.2 Treatment Period

Each subject visits the Investigative site at the beginning of the study for Visit 1 (Week 1) and the matched wounds are randomized (if entry criteria are met) and the assessment/treatment period begins and will continue for another 25 weeks. Additionally, the subject will return to the Investigative site for a single day Safety Follow-up Visit 30 days (± 4 days) from the last dose of B-VEC.

3.1.2.1 Guidance for Subjects Enrolled under Previous Protocol Versions

Subjects enrolled under previous protocol versions, in which more than one (1) Primary Wound Pair was selected, will continue to receive their randomized treatment for the duration of the study. However, the Investigator will select a single matched pair, which most closely match in both size and anatomical location. This single Primary Wound Pair will be used for evaluation and will be included in the outcome measurements.

3.1.3 Number of Subjects and Interim Analysis

With 90% power and a two-sided Type 1 error rate of 5%, 24 subjects (i.e., 24 wound pairs) are required for a McNemar's test, assuming a response rate of 75% among wounds randomized to B-VEC and a response rate of 25% among wounds randomized to placebo. These response rates are supported by the results of a Phase 1/2 study in which the response rates for weeks 10 and 12 were 71% and 83% for active and 33% and 14% for placebo, respectively. Because the sample size calculation assumes no correlation within subjects, the estimate is conservative. Any positive correlation will cause an increase in power for the sample size of 24. PASS 2020, "Tests for Two Correlated Proportions (McNemar Test)", was used to calculate the sample size. Because of the small n, the multinomial enumeration was used instead of the normal approximation.

If we assume a 75% response rate among wounds randomized to B-VEC and a 25% response rate among wounds randomized to placebo and we assume independence among the wounds within a subject, we expect a total of 62.5% discordant pairs. Under this scenario, 18.75% of the subjects will have positive responses for both wounds and 18.75% will have negative responses for both wounds:

Expected rates of response and non-response, assuming a 75% response rate for B-VEC treated wounds, a 25% response rate for placebo-treated wounds and no correlation between wounds. The off-diagonals correspond to discordant pairs.

		Placebo		
		Response	Non-response	Total
B-VEC	Response	18.75%	56.25%	75.00%
	Non-response	6.25%	18.75%	25.00%
	Total:	25.00%	75.00%	100%

[figure not shown]
Interim analyses will not be performed for this study.

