7.2 Primary Efficacy Analysis

The primary efficacy analyses will use the ITT population and the Primary Wound Pair.

The primary endpoint is the proportion of DEB primary wound sites with complete wound healing from baseline in B-VEC-treated and placebo-treated intra-subject wound sites at Weeks 22 and 24 or 24 and 26, as determined by the Investigator. Complete wound healing is defined as 100% wound closure from the exact wound area selected at baseline, specified as skin re-epithelialization without drainage:

The primary endpoint is defined as responder wounds that meet any of the following conditions:

- Healed on Week 22 and Week 24, or
- Healed on Week 24 and Week 26

Only wounds that are healed for at least two (2) consecutive weeks are counted as positive responses. The primary endpoint response data will be summarized descriptively by the wound treatment.

A summary of the outcomes for each member of the Primary Wound Pair can be represented in the following 2x2 table, where each entry represents a subject. T is the total number of subjects in the ITT population and each cell entry is the number of subjects with the corresponding outcomes of the Primary Wounds.

		Placebo		Row total
		Complete Wound Healing	No Complete Wound Healing	
B-VEC	Complete Wound Healing	A	B	N1
	No Complete Wound Healing	C	D	N2
Column total		M1	M2	T

The null hypothesis of interest is the absence of a treatment effect on wound healing and the alternative hypothesis is the presence of a treatment effect on wound healing.

These hypotheses are equivalent to the following null and alternative hypotheses:

Null Hypothesis H0: Prob(B) = Prob(C)

Alternate Hypothesis H1: Prob(B) ≠ Prob(C)

Where Prob(B) and Prob(C) are the probability of the occurrence of discordant pairs B (B-VEC=Positive & PBO=Negative) and C (B-VEC=Negative & PBO=Positive).

The null hypothesis will be tested by a McNemar test statistic using a two-sided type I error rate of 0.05:

$$\chi^2_{\text{McNemar}} = (B - C)^2 / (B + C)$$

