Under the null hypothesis of no difference between the proportions of the two possible types of discordant pairs, this test statistic follows a chi-square distribution with 1 degree of freedom. If the total number of discordant pairs (B+C) are sufficiently small (less than 6), the McNemar test with a continuity correction will be used. If the chi-square test result is significant, the null hypothesis of no treatment difference will be rejected in favor of the alternative hypothesis that a treatment difference exists.

In addition to testing the null hypothesis, the McNemar odds ratio and its 95% confidence interval will be summarized to indicate the magnitude of the treatment effect with B-VEC treatment. The McNemar odds ratio is the ratio of the counts of the discordant pairs B and C.

For subjects with missing primary endpoint data, a multiple imputation approach (details see section [7.1.6](#)) assuming MAR will be used.

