7.3 Key Secondary Efficacy Analysis

The key secondary efficacy analyses will be based on the ITT population. The primary efficacy analyses will be repeated for responder wounds that meet any of the following conditions:

- Healed on Week 8 and Week 10, or
- Healed on Week 10 and Week 12.

Only wounds that are healed for at least two (2) consecutive weeks are counted as positive responses. The key secondary endpoint response data will be summarized descriptively by the wound treatment.

The McNemar testing procedure used for the primary endpoint will be repeated for this key secondary endpoint. A multiple imputation approach (details see section [7.1.6](#)) assuming MAR will be used to impute missing endpoint data. If the primary endpoint is statistically significant at a type I rate of 0.05, the same full type I rate of 0.05 will be passed on to evaluate the key secondary endpoint.

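### Does the 24-pair sample size in SAP 3.1.3 fail to match the McNemar test planned in SAP 7.2?

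*SAP*

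**What the plan says.** SAP 3.1.3 bases the size of the trial on a McNemar test with 75% response on B-VEC, 25% on placebo and no within-subject correlation: "With 90% power and a two-sided Type 1 error rate of 5%, 24 subjects (i.e., 24 wound pairs) are required". Its table of expected rates puts 56.25% of subjects in the cell where only the B-VEC wound heals and 6.25% in the cell where only the placebo wound heals. It names PASS 2020 and the correlated-proportions module, and adds: "Because of the small n, the multinomial enumeration was used instead of the normal approximation". It does not state whether the rejection rule was exact or asymptotic, and it gives no attained power. Protocol 8.3 and the Synopsis repeat the 24 pairs and the 90%.

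SAP 7.2 sets the primary test: "The null hypothesis will be tested by a McNemar test statistic using a two-sided type I error rate of 0.05". The statistic is (B − C)²/(B + C) on 1 degree of freedom, with one exception: "If the total number of discordant pairs (B+C) are sufficiently small (less than 6), the McNemar test with a continuity correction will be used". SAP 7.3 carries the method over: "The McNemar testing procedure used for the primary endpoint will be repeated for this key secondary endpoint".

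**The concern.** SAP 3.1.3 turns away from the normal approximation because the sample is small. SAP 7.2 then refers the primary statistic to a large-sample chi-square distribution at that same sample size. Someone reading 3.1.3 alone could expect exact inference and be surprised by 7.2.

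Two things would be at stake. First, if 24 pairs were sized for one test and another is used, the power statement might not describe the trial. Second, at this sample size the two forms can disagree on a close result. Discordant splits of 9-2, 11-3 and 12-4 are significant by SAP 7.2 but not by the exact test. None of the sensitivity analyses in SAP 7.2.1 or 7.3.1 changes the reference distribution. They change the population or the handling of missing outcomes; for example, the analysis "for the primary efficacy endpoint will be repeated with observed data without any imputations for missing values".

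**Working it through.** **Inputs (SAP 3.1.3 and 7.2).** Probability of a B-VEC-only pair: 0.75 × 0.75 = 0.5625. Probability of a placebo-only pair: 0.25 × 0.25 = 0.0625. Total discordance: 0.5625 + 0.0625 = 0.625. Two-sided level 0.05; all pairs complete.

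**Method.** For n pairs, the number of discordant pairs m follows Bin(n, 0.625). Given m, B follows Bin(m, 0.5625/0.625 = 0.9), and C = m − B. Power is the sum of the probabilities of all (B, C) that the test rejects.

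- Exact rule: reject if 2 × P(Bin(m, 0.5) ≤ min(B, C)) ≤ 0.05.
- SAP 7.2 rule: reject if the chi-square p-value of (B − C)²/(B + C) is at most 0.05, with the continuity correction when B + C < 6. That exception has probability 0.004% at n = 24 under the design, so the planned test is in effect the uncorrected chi-square.

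**Power, with the plan's own figure reproduced first.**

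| Pairs | Exact McNemar | SAP 7.2 rule |
|---|---|---|
| 20 | 82.6% | 88.4% |
| 21 | 84.9% | 90.1% |
| 22 | 87.0% | 91.6% |
| 23 | 88.8% | 92.9% |
| 24 | 90.5% | 94.1% |

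Twenty-four is the minimum for 90% under the exact test, so the SAP's number is reproduced. Under the SAP 7.2 rule the minimum is 21, leaving 24 − 21 = 3 spare pairs. Other variants do not have 24 as their minimum: a chi-square test corrected throughout needs 25 (89.7% at 24), mid-p needs 21, the one-sided exact test needs 20, and the normal-approximation formula gives 21.8, or 22.

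**Where the two tests disagree at n = 24.** The main splits are below. The chi-square value for 9-2, for example, is (9 − 2)²/11 = 4.45.

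| Split | SAP 7.2 p | Exact p | Mid-p | Probability under the design |
|---|---|---|---|---|
| 9-2 | 0.035 | 0.065 | 0.039 | 0.9% |
| 11-3 | 0.033 | 0.057 | 0.035 | 1.7% |
| 12-4 | 0.0455 | 0.077 | 0.049 | 0.8% |

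All disagreeing splits together have probability 3.6% under the design alternative. The reverse case, exact significant and SAP 7.2 not, never occurs.

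**Type I error at n = 24.** If wounds are independent with a common healing rate p, null discordance is 2p(1 − p): 0.375 at p = 0.25 and 0.50 at p = 0.50, which is its maximum.

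| Null discordance | SAP 7.2 rule | Exact |
|---|---|---|
| 0.375 | 3.8% | 2.1% |
| 0.50 | 4.3% | 2.4% |
| 0.625 | 4.8% | 2.8% |
| 0.69 | 5.0% | 3.0% |
| 1.00 | 6.4% | 2.3% |

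The planned test passes 5% only from about 69% null discordance. That lies above the 50% ceiling for independent wounds, so it would need negatively correlated outcomes within a subject.

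**The case for a change.** The best case for acting is that the arithmetic is sound and the remedy cheap. The text of SAP 3.1.3 fits an exact test, the SAP gives a small-sample argument there and does not follow it in 7.2, and every disagreement between the two tests favours the test that was chosen. An exact sensitivity analysis can be prespecified only before unblinding.

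The arithmetic stands in full, but the inference to a fault in the plan does not. No two sections contradict each other: 3.1.3 says only that a McNemar test was used, and 7.2 specifies a McNemar test. That the software enumerated the exact rule is inferred from 24 being that rule's minimum. Enumerating the multinomial outcomes is also a way to compute power, and it can be applied to an asymptotic rejection rule as readily as to an exact one, so the remark about the small sample does not commit the sponsor to exact inference.

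The borderline splits look worrying mainly because the exact test is conservative: its true size is 2.1% to 2.4% where the planned test has 3.8% to 4.3%, against a nominal 5%. Mid-p, which removes much of that conservatism, agrees with SAP 7.2 at 9-2, 11-3 and 12-4. Up to 24 discordant pairs it departs from the planned rule only at 5-0 and 15-6. Adding an exact analysis would be a reasonable preference, but it corrects nothing.

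**Conclusion.** The concern does not call for a change. SAP 3.1.3 omits one detail, the McNemar form behind the 24 pairs, and that detail can be recovered with reasonable confidence by calculation. The test that will be run has 94.1% power where 90% is claimed, and it keeps at least 90% down to 21 complete pairs. The plan adds nothing for dropout, so the three spare pairs are a useful margin. Type I error is at or below 4.3% for independent wounds with a common healing rate of 25% to 50%. Protocol 8.3 and the Synopsis name no formula and are not wrong as they stand.

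The assumptions are these. The figures use complete pairs and the SAP's independence assumption. Positive within-subject correlation raises power. Negative correlation lowers it: if both wounds heal in 15% of subjects rather than 18.75%, the SAP 7.2 test has 89.9% power at 24. SAP 7.2 also provides: "For subjects with missing primary endpoint data, a multiple imputation approach". Power after that pooling was not worked out here, and the documents do not report it. One figure in SAP 3.1.3 could not be read, so it cannot be ruled out that the form of the test is named there. None of this alters the sample size, the primary test or how its result would be read.
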